6.5.2. Dose Intensity and Relative Dose Intensity of Rituximab

Actual dose intensity (mg/m²): the actual dose to which the participant was exposed. The ADI per infusion will be derived as follows:

- If the question regarding whether the participant was given the protocol standard 375 mg/m² dose was answered with
 - Yes

Actual rituximab dose level $(mg/m^2) = 375 \text{ mg/m}^2$

- No

Actual rituximab dose level (mg/m^2) = total prepared dose (mg) / participant BSA (m^2) on Day 1 of the cycle

- If the question "was the entire infusion administered" on the "Rituximab Infusion" eCRF page answered with
 - Yes

ADI at the visit = actual rituximab dose level (mg/m^2)

- No

ADI at the visit = actual rituximab dose level $(mg/m^2) \times (actual volume administered / planned volume)$

- Skipped doses will result in an ADI of 0 for the particular visit.
- The ADI will be calculated by summing up all infusion-wise actual doses.

Planned dose intensity (mg/m²): The planned dose is 375 mg/m² as per Protocol.

Relative dose intensity (%): The RDI expresses the amount of drug administered compared with the planned amount of drug across all infusions.

 $RDI = ADI / (PDI \times the number of infusions) \times 100$

6.5.3. Dose Intensity and Relative Dose Intensity of Lenalidomide

Actual dose intensity (mg): the actual dose the participant was exposed to (this is captured in "Study Drug Administration - Lenalidomide" eCRF form).

Planned dose intensity (mg): The planned dose is 20 mg QD on Days 1 to 21 of each cycle. A participant with moderate renal insufficiency will receive a starting dose of 10 mg daily on the same schedule. After 2 cycles, if no lenalidomide-related toxicities of Grade 3/4 occur, the planned dose may be increased to 15 mg QD on Days 1 to 21 of each cycle.

Relative dose intensity (%): The RDI expresses the amount of drug administered compared with the planned amount of drug at all time.

 $RDI = ADI / PDI \times 100$

6.6. Lenalidomide Compliance

For participants in the safety population, overall compliance (%) for lenalidomide will be calculated for all participants as follows:

Compliance (%) = $100 \times \text{(total dose actually taken)} / \text{(total prescribed dose)}$.

The total prescribed dose is defined as the sum of the doses prescribed by the INV accounting for dose modifications.

The total actual dose taken will be calculated based on drug dispensing information and/or administration information entered on the "Study Drug Administration - Lenalidomide" eCRF form.

If the drug accountability data are not appropriately collected, relative dose intensity is considered as an approximation of lenalidomide compliance and will be used as surrogate.

6.7. Dose Modifications

Dose reductions of tafasitamab or placebo are not permitted. Delaying the tafasitamab or placebo dose is permitted for no more than 2 days. Alternatively, a tafasitamab or placebo infusion may be skipped completely, and the next scheduled dose will be administered. Tafasitamab/placebo administration can also be interrupted during infusion. The number and percentage of participants with a dose interruption, dose delay, or skipped dose of tafasitamab/placebo will be

summarized by treatment group. The reason for dose interruption/delay/skipped will be summarized as captured on the "Tafasitamab/Placebo Infusion" eCRF page.

The lenalidomide dose can be either interrupted or reduced per the dose levels in Table 5. The number and percentage of participants with lenalidomide dose interruptions/reductions and the lowest dose level achieved per participant will be summarized by treatment group. Reasons for dose interruptions/reductions for lenalidomide will be summarized as captured on the "Study Drug Changes - Lenalidomide" eCRF page.

Table 5: Dose Reduction Steps for Lenalidomide

Starting dose	tarting dose 20 mg QD on Days 1-21, every 28 days	
Dose level -1	15 mg QD on Days 1-21, every 28 days	
Dose level -2	10 mg QD on Days 1-21, every 28 days	
Dose level -3	5 mg QD on Days 1-21, every 28 days	

Dose modifications of rituximab are not mandated unless clinically indicated as per the SmPC, the USPI, and applicable institutional guidelines (MabThera 2020, Rituxan 2020). The number and percentage of participants with a dose interruption, dose delay, or skipped dose of rituximab will be summarized by treatment group. The reason for dose interruption/delay/skipped will be summarized as captured on the "Rituximab Infusion" eCRF page.

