6. STUDY TREATMENT

6.1. Study Treatments Administered

A treatment cycle is defined as 28 calendar days and includes treatment with tafasitamab/placebo, lenalidomide, and rituximab. The treatment period for each participant starts with the first administration of study treatment on Cycle 1, Day 1 (C1D1). Study drugs are tafasitamab/placebo, lenalidomide, and rituximab. Tafasitamab, lenalidomide, and rituximab are considered IMPs (see Table 7).

Tafasitamab (12 mg/kg IV) or placebo (0.9% saline solution IV)

- Administered Cycles 1 to 3 on Days 1, 8, 15, and 22, and Cycles 4 to 12 on Days 1 and 15.
- Tafasitamab will be supplied by the sponsor to an unblinded pharmacy. The placebo will be locally sourced and delivered to an unblinded pharmacy. In case of changes in body weight, tafasitamab dosing should be based on the participant's weight as assessed at the most recent treatment cycle.

Rituximab (including biosimilars; 375 mg/m² IV)

- Administered Cycle 1 on Days 1, 8, 15, and 22, and Cycles 2 to 5 on Day 1.
- Rituximab should be administered approximately 30 minutes after the tafasitamab/placebo infusion is completed but no less than 15 minutes. Sites have the option for the sponsor to provide rituximab via the IRT. Rituximab may also be obtained by the sites, where applicable. For logistical reasons, rituximab may be administered on the day after the tafasitamab infusion, or administration may be split over 2 consecutive days, according to local practice and the institution's standard of care.

Lenalidomide (including generics) (20 mg PO QD*)

- Administered Cycles 1 to 12 on Days 1 to 21 at approximately the same time every day. Lenalidomide will be provided by the sponsor to the sites.
- *For participants with moderate renal insufficiency (creatinine clearance ≥ 30 mL/min to < 60 mL/min), the starting dose of lenalidomide must be reduced to of 10 mg daily using the same schedule. The dose of lenalidomide may be increased to 15 mg QD on Days 1 to 21 of each cycle if no Grade 3/4 lenalidomide-related toxicities occur after 2 cycles.

Table 7 presents the study treatment information.

Table 7: Study Treatment Information

	Study Treatment 1	Study Treatment 2	Study Treatment 3
Study treatment name:	Tafasitamab	Lenalidomide	Rituximab

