5.2. Treatment Groups

This is a randomized, double-blind, parallel treatment group design. Participants will be summarized by treatment group (see Table 3) for the FL and MZL populations separately and for the overall population.

Table 3: Treatment Groups, Dose Paradigm, and Cycle Length

TGA	TGB
Tafasitamab:	Matching placebo (0.9% saline solution):
12 mg/kg IV on Days 1, 8, 15, and 22 of Cycles 1 to 3 and on Days 1 and 15 (every second week) of Cycles 4 to 12. Cycle length is 28 days.	IV on Days 1, 8, 15, and 22 of Cycles 1 to 3 and on Days 1 and 15 (every second week) of Cycles 4 to 12. Cycle length is 28 days.

Rituximab (including biosimilars):

 $375 \text{ mg/m}^2 \text{ IV}$ every week in Cycle 1 on Days 1, 8, 15, and 22 and on Day 1 of every 28-day cycle from Cycles 2 to 5.

Note: rituximab should be administered approximately 30 minutes after the tafasitamab/placebo infusion is completed. For logistical reasons, rituximab may be administered on the day after the tafasitamab infusion, or administration may be split over 2 consecutive days, according to local practice and the institution's standard of care.

Lenalidomide (including generics):

20 mg PO QD on Days 1 to 21 of every 28-day cycle for 12 cycles.

Note: a participant with moderate renal insufficiency (creatinine clearance ≥ 30 mL/minute to < 60 mL/minute) will receive a starting dose of 10 mg daily on the same schedule. After 2 cycles, if no lenalidomide-related toxicities of Grade 3/4 occur, the dose may be increased to 15 mg QD on Days 1 to 21 of each cycle.

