6.4. Exposure

For participants in the safety population, exposure to tafasitamab, lenalidomide, and rituximab will be summarized descriptively as follows. Lenalidomide exposure will also be displayed by creatinine clearance group (≥ 30 and < 60 mL/minute vs ≥ 60 mL/minute).

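### The lowest-dose-level summary for lenalidomide is anchored at a 20 mg start, so participants who start at 10 mg for renal insufficiency share rows with 20 mg starters reduced two or three levels

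*SAP*

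**What the plan says.** SAP Section 6.7 ties lenalidomide changes to one ladder: "The lenalidomide dose can be either interrupted or reduced per the dose levels in Table 5". In Table 5 the starting dose is "20 mg QD on Days 1-21, every 28 days", level -1 is 15 mg, level -2 is "10 mg QD on Days 1-21, every 28 days" and level -3 is 5 mg. Protocol Appendix B has the same four steps. Section 6.7 then plans two separate items: how many participants had an interruption or reduction, and how low each participant went, where "the lowest dose level achieved per participant will be summarized by treatment group".

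The renal start is stated in several places. Protocol Section 6.1 says that for creatinine clearance from 30 to below 60 mL/min "the starting dose of lenalidomide must be reduced to of 10 mg daily using the same schedule". SAP Section 5.2 says such a participant "will receive a starting dose of 10 mg daily on the same schedule". Both allow an increase to 15 mg after two cycles without Grade 3/4 lenalidomide-related toxicity. SAP Section 6.5.3 carries the rule into the planned dose: "A participant with moderate renal insufficiency will receive a starting dose of 10 mg daily on the same schedule".

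SAP Section 6.4 adds that "Lenalidomide exposure will also be displayed by creatinine clearance group", and Section 8.2.4 splits adverse events leading to lenalidomide reduction in the same way. Section 6.7 names neither the renal start nor that split.

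**The concern.** On the Table 5 scale a level is a distance below 20 mg. For someone assigned 20 mg, that distance shows how far the dose was reduced. For someone assigned 10 mg it does not: two of the levels are there on the first day because of kidney function. Pooling both groups in one table by treatment group makes level -2 and level -3 uninterpretable as measures of tolerability.

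How far the lenalidomide backbone had to be lowered when tafasitamab is added is a reasonable question to ask of this trial, and this summary is one of the places a reader would look. Renal starters add roughly the same amount to the lower rows of both arms. That raises the apparent extent of reduction in each arm and slightly narrows any difference between them.

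**Working it through.** **Inputs from the documents.** Table 5 scale (SAP 6.7): 20 mg = 0, 15 mg = -1, 10 mg = -2, 5 mg = -3. Renal start 10 mg, with a possible increase to 15 mg (Protocol 6.1; SAP 5.2 and 6.5.3). About 618 participants randomized (Protocol, Table 2).

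**Step 1: run dose paths through the scale.** For each path, take the lowest dose, read its Table 5 level, count the actual reductions, and subtract the level of the participant's own starting dose.

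| Dose path (mg) | Lowest Table 5 level | Actual reductions | Levels relative to own start |
|---|---|---|---|
| 20, unchanged | 0 | 0 | 0 |
| 20 to 15 | -1 | 1 | -1 |
| 20 to 15 to 10 | -2 | 2 | -2 |
| 10, unchanged | -2 | 0 | 0 |
| 10 to 15 | -2 | 0 | 0 |
| 10 to 15 to 10 | -2 | 1 | 0 |
| 10 to 5 | -3 | 1 | -1 |
| 10 to 15 to 10 to 5 | -3 | 2 | -1 |

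Level -2 holds people with zero, one and two reductions. Every 10 mg starter is at level -2 or lower by construction. Protocol Appendix B treats a move from 10 to 5 mg as one step down, yet the summary would show it at level -3.

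**Step 2: how many people.** The documents give no share with moderate renal insufficiency, so I assume 5% to 20%:
- 618 × 0.05 = 30.9, about 31
- 618 × 0.10 = 61.8, about 62
- 618 × 0.20 = 123.6, about 124

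These are all participants placed at level -2 or lower because of their start. They are an upper bound on those placed there with no reduction, because some 10 mg starters will have a real one.

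**Step 3: effect on the displayed share.** Let s be the share starting at 10 mg and r the share of 20 mg starters whose dose falls to 10 mg or below; both are assumed. The share shown at level -2 or lower is s + (1 - s) × r. The part of it made up of 20 mg starters who were reduced is (1 - s) × r.
- s = 0.05, r = 0.10: shown 0.145; reduced 20 mg starters 0.095
- s = 0.10, r = 0.10: shown 0.19; reduced 20 mg starters 0.09
- s = 0.20, r = 0.20: shown 0.36; reduced 20 mg starters 0.16

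**Step 4: effect on the comparison of arms.** If s is equal in both arms, the displayed difference is (1 - s) times the difference among 20 mg starters. A 10-point difference becomes 9 points at s = 0.10 and 8 points at s = 0.20. The direction does not change.

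**The case against.** The strongest reply is that the layout has not been seen. Table shells are in a separate document, and SAP Appendix A lists no table devoted to the lowest dose level. If the rows are in mg, 10 mg for a 10 mg starter is simply correct. If the item sits with the exposure tables, Table 3.1.4.x may already split it by creatinine clearance. That may be so, but Section 6.7 speaks of dose levels, defines them from 20 mg and asks for a summary by treatment group. The text as it stands leads to the mixed rows, and nothing in it prevents them.

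The reply is also right that lenalidomide tolerability does not rest on this one item. Relative dose intensity uses a planned dose that recognises the 10 mg start. Reductions and their reasons come from the lenalidomide changes page of the eCRF. Adverse events leading to reduction, interruption and discontinuation are tabulated separately. Safety is not formally tested.

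A reader might infer that every 10 mg starter is reported as reduced without having been reduced, or that this summary conflicts with the reduction count. The documents do not support either. Nothing codes a 10 mg start as a reduction, so the count is not inflated. The count and the lowest level are different quantities. Some 10 mg starters do have a true reduction, as in the 10 to 5 mg and 10 to 15 to 10 mg paths.

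**Conclusion.** The point holds as a narrow reporting matter. Applied as written, the lowest-level summary puts a 10 mg starter who was never reduced, or who was escalated, in the same row as a 20 mg starter reduced twice. It also shows a single step from 10 to 5 mg at level -3.

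One descriptive safety summary is affected; efficacy analyses and error rates are not. Randomization is not stratified by renal function, but it should spread 10 mg starters about evenly, so the effect should be similar in both arms and should not favour either.

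The size cannot be fixed from the documents. The range of 31 to 124 participants, and the displayed shares above, rest on assumed proportions. The conclusion also rests on reading Section 6.7 literally, because the shells are not available.

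**What to change.** In SAP Section 6.7, state that the lowest lenalidomide dose will be presented in mg, by treatment group, separately for participants assigned a 20 mg start and those assigned a 10 mg start. The creatinine clearance groups already used in SAP Section 6.4 would serve equally well for the split. Keep the separate count of participants with reductions: a 10 to 15 to 10 mg path shows no net step below the starting dose although one reduction took place.

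This changes reporting only. Table 5, Protocol Appendix B and all dosing rules stay as they are. No new data are needed. The cost is a sentence in the SAP and one additional split of a descriptive table.

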6.8. Prior and Concomitant Medication

Prior medications and concomitant medications will be coded using the WHO Drug Dictionary. The number and percentage of participants in the FAS for each prior and concomitant medication will be summarized by WHO drug class and WHO drug PT.

Premedication given prior to tafasitamab/placebo administration to mitigate potential infusion-related reactions will be listed.

7. EFFICACY

Appendix A provides a list of data displays. Sample data displays are included in a separate document.

7.1. General Considerations

All efficacy analyses will be based on the FAS. Unless otherwise stated, all stratified efficacy analyses will use the same stratification factors as for randomization, which are specified in Section 3.1 and based on the data obtained from IRT.

7.2. Efficacy Hypotheses

The primary hypothesis is that tafasitamab in combination with lenalidomide and rituximab will improve PFS compared with lenalidomide and rituximab alone in participants with R/R FL. Assume $S_1(t)$ is the survival function of tafasitamab in combination with lenalidomide and rituximab, and $S_2(t)$ is the survival function of lenalidomide and rituximab alone. The hypotheses of the study are as follows:

- H₀ (null hypothesis): $S_1(t) = S_2(t)$
- H_A (alternative hypothesis): $S_1(t) \neq S_2(t)$

7.3. Analysis of the Primary and Key Secondary Efficacy Endpoints

7.3.1. Primary Efficacy Analysis for Progression-Free Survival in Follicular Lymphoma

Progression-free survival by INV assessment is defined as the time from the date of randomization to the date of first documented disease progression, as determined by disease assessment per the Lugano classification (Cheson et al 2014) or death due to any cause, whichever occurs earlier. For the primary analysis, PFS will be censored if no PFS event is observed before the cutoff date or the date that a new antilymphoma therapy is started. Censoring for PFS will follow the algorithm outlined in Table 6, which is based on the FDA Guidance (FDA 2015, FDA 2018).

Table 6: Evaluation and Censoring of Progression-Free Survival

Situation	Date of Progression or Censoring	Outcome	Censoring Reason
No baseline tumor assessments	Date of randomization	Censored	No baseline assessment
No valid postbaseline response assessments	Date of randomization	Censored	No postbaseline assessment
Progression documented between scheduled response assessments	Date of first overall response of PD	Progressed	Not applicable
No progression	Date of last adequate tumor assessment (not NE and not missing) prior to cutoff date	Censored	Ongoing
Study discontinuation without documented progression	Date of last adequate tumor assessment (not NE and not missing) prior to cutoff date	Censored	Study discontinuation
New antilymphoma treatment started	Date of last adequate tumor assessment with no documented progression (not NE and not missing) on/before starting a new antilymphoma treatment	Censored	Start of new antilymphoma treatment
Death before first progressive response assessment	Date of death	Progressed	Not applicable
Death between adequate response assessments	Date of death	Progressed	Not applicable
Death or progression after 2 or more missed assessments	Date of last progression assessment with documented nonprogression	Censored	Death or PD after 2 or more missed assessments

The date of last adequate tumor assessment is the date of the last tumor assessment with an overall lesion response of CR, PR, or SD. In this case, the last tumor evaluation date at that assessment is used. If a PFS event is observed after a single missing or nonadequate tumor assessment, the actual date of event will be used, as per the Lugano classification (Cheson et al 2014).

The distribution of PFS by INV assessment will be compared between the 2 treatment groups using a stratified log-rank test at 2-sided 5% level of significance. The strata information will be based on the data obtained from IRT that was used for randomization.

A stratified Cox proportional hazard model will be used to estimate the HR between TGA (tafasitamab + lenalidomide + rituximab) versus TGB (placebo + lenalidomide + rituximab), along with 2-sided 95% CI.

The distribution of PFS will be estimated using the Kaplan-Meier method. The number of events, censoring, and censoring reasons will be summarized. The median along with 2-sided 95% CIs will be presented by treatment group. The 95% CI will be calculated using the generalization of Brookmeyer and Crowley's method (1982) with log-log transformation

(Klein and Moeschberger 1997). In addition, PFS rates at 6, 12, 18, 24, 36, and 48 months may be provided along with the corresponding 2-sided 95% CIs.

All analyses mentioned above will be performed for participants with FL in the FAS.

If the null hypothesis is rejected at a 2-sided significance level of 5%, the primary endpoint is met. Alpha of 5% will be passed down to test the key secondary endpoints per the hierarchical testing order specified in Section 7.3.2. The p-value obtained from the stratified log-rank test for PFS in the FL population of the FAS will be used for hierarchical testing.

If a participant was randomized into the MZL cohort but after randomization was confirmed by the site to have a diagnosis of FL, the eCRF-derived information for medical history will be used to derive the 2 missing stratification factors for the FL cohort: POD24 status (yes versus no) and refractoriness to prior anti-CD20 mAb therapy (please refer to the definition in Section 3.1). If a participant was randomized into the FL cohort but after randomization was confirmed by the site to have a diagnosis of MZL, the IRT-derived stratification factor needed for this cohort (number of prior lines of therapy: < 2 versus ≥ 2) will be used.

7.3.2. Analyses of Key Secondary Efficacy Endpoints

As specified in Section 3.2, a hierarchical testing procedure will be implemented for the key secondary endpoints, with the primary endpoint PFS serving as a gatekeeper. This hierarchical testing procedure will maintain the study-wise Type I error rate at 2-sided 5%. If the primary null hypothesis is rejected, the key secondary endpoints can be tested in the following fixed order:

- 1. PFS by INV in the overall population (FL and MZL)
- 2. PET-CR rate by INV in the FDG-avid FL population
- 3. OS in the FL population

7.3.2.1. Progression-Free Survival in the Overall Population

Progression-free survival by INV assessment in the overall population (FL and MZL) will be compared and analyzed in the same manner as described in Section 7.3 for the PFS in the FL population. The strata information for the stratified log-rank test will be based on the randomization factor used for both cohorts, FL and MZL: number of prior lines of therapy ($< 2 \text{ versus} \ge 2$).

The p-value obtained from the stratified log-rank test for PFS in the overall population, using the strata information based on IRT that was used for randomization, as well as stratification by FL versus MZL, will be used for hierarchical testing.

As mentioned in Section 7.3, participants with different initial diagnosis by INV and in the IRT will be considered as mentioned in the eCRF.

7.3.2.2. Positron-Emission Tomography-Complete Response Rate in the FDG-Avid Follicular Lymphoma Population

The PET-CR rate is defined as the proportion of FDG-avid participants who achieved a CR as per Lugano classification (Cheson et al 2014) with a PET-negative result defined as a complete metabolic response at any time after start of treatment over the FDG-avid FL population at baseline. FDG-avid FL participants with no postbaseline assessment by PET or those who did not achieve a PET-CR will be classified as "non-CR-responder."

The CR rate will be compared between the 2 treatments groups using a stratified CMH test. The odds ratio and its 95% CIs calculated from the stratified CMH test will also be presented. The number of participants classified as PET-CR responders and the respective rates as well as 95% CIs (using Clopper-Pearson) will be presented.

Analysis of the key secondary endpoint of PET-CR will be performed for participants with FDG-avid FL in the FAS. If the null hypothesis is rejected at a 2-sided significance level of 5%, this key secondary endpoint is met. The p-value obtained from the CMH test for PET-CR rate by INV assessment in the FDG-avid FL population, using the strata information based on IRT that was used for randomization, will be used for hierarchical testing.

